11.1. Appendix 1: Schedule of Events (SoE) / Milestones

Schedule of Events

Measures	Visit (Weeks)											
	Baseline	2	4	6	8	10	12	14	16	18	20	22
Age/Gender/Gender Identity/Insurance Type (Public, Private, No Insurance)/Ethnicity (Hispanic, Non Hispanic)/ Race (African American, Non African American)/ Living Situation (One Parent, Both Parents, Other)												
Demographics Form	x											
Severity of Suicidal Ideation												
CHRT-SR (self-report)-14 item	x	x	x	x	x	x	x	x	x	x	x	x
Suicidal Events												
Suicidal Event Form for START	x	x	x	x	x	x	x	x	x	x	x	x
Substance Use												
Clinical Features (CF)	x	x	x	x	x	x	x	x	x	x	x	x
Treatment Satisfaction												
Client Satisfaction Questionnaire (CSQ-8)		x										
Satisfaction with Life												
PROMIS Short Form-Life Satisfaction (SL)	x	x	x	x	x	x	x	x	x	x	x	x
PROMIS Parent-Proxy SL-Short Form 8a	x	x	x	x	x	x	x	x	x	x	x	x
PROMIS Pediatric SL-Short Form 4a	x	x	x	x	x	x	x	x	x	x	x	x
Other												
COVID-19 Survey		x										
Self Assessment Manikin (SAM)	x						x

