2.3. Benefit/Risk Assessment

Potential Benefits to Participants: The benefits of participation include having an increased level of safety monitoring which involves gathering data from parents and participants every two weeks for up to 180 days. Participants and their parents will receive monitoring that is likely to be more intensive than what would be available in the community. Overall, safety may improve for participants in all treatment groups when compared to adolescents with suicidality who are not in this study. All of this monitoring will be provided at no cost to the participants and their families. Research project staff will be on call during business hours for participants in all treatment groups. We will check in with patients in person or with phone calls as needed. Phone calls or in person visits will occur depending on whether research staff feel that it is needed based on participant responses to scales and questionnaires. If safety concerns are identified during follow survey completion, including suicidal behavior or an increase in suicidal ideation based on questions 13-14 on the CHRT-SR, an automated text message or email will be sent to guardians identifying the safety concern and providing emergency numbers if needed. Research staff will then attempt to contact legal guardian to encourage follow up with patient's clinical team and provide referrals if needed. If serious safety concerns are identified, including significantly worsening suicidal thoughts or suicidal behaviors, family will be referred to the ED. Text messaging may also be used as a reminder of study participation and/or to notify that further communication by phone or in person is needed. Study related questions or safety concerns may be addressed via text messaging, email, phone calls or in person communication. Participants may derive a sense of accomplishment from participation in research and contributing to the knowledge of treatment of adolescents with suicidality.

Potential Benefits to Others: Potential benefits to society may be considerable.

Information will be provided about the outcomes and treatment satisfaction of telehealth CIS, OCIC, and inpatient for adolescents with suicidality. If telehealth CIS and/or OCIC is found to have the same or better outcome to inpatient within our study population group of patients with

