Breach of confidentiality: There is a potential risk of loss of confidentiality. Consistent with the Federal guidelines, all patients and guardians will be informed of the federally mandated reporting laws for child abuse and neglect, verbally and in the written consent form. Therefore, if abuse or neglect is suspected, per institutional and legal standards and requirements, the Department of Human Services may be called if appropriate and indicated. Risks associated with this reporting include embarrassment, legal consequences, and removal of the child from home.

3. Specific Aims and Hypothesis

Specific Aims	Hypothesis

SA1: Evaluate the safety of CIS-telehealth relative to inpatient and OCIC-in-person among children with similar CHRT-SR scores.
	
 Our working hypothesis is that CIS-telehealth is associated with a greater risk of suicidal event relative to inpatient and in-person OCIC. Response is defined by a delay in first recurrence of a suicidal event and a lower number of suicidal events over 90 days and 180 days. Clinical Features: 
 Severity of suicidal ideation at baseline and over 180 days number of suicidal events at baseline only Substance use at baseline and over 180 days. Sociodemographic features: Age, Gender, Gender Identity, Type of insurance (Public, Private or none), Ethnicity, Race, or living with one biological parent, two biological parents, a stepparent, a relative, or other.

SA2: Examine the effectiveness of CIS-telehealth relative to inpatient and in-person OCIC among children with similar CHRT scores.
	
 Our working hypothesis is that CIS-telehealth will be associated with poorer reduction in emotional arousal and perceived stress levels in response to COVID-19 the pandemic relative to CIS-inpatient and CIS-in-person.

SA3: Assess patient and parent treatment satisfaction with CIS-telehealth relative to inpatient and in-person OCIC among children with similar CHRT scores.
	
 Our working hypothesis is that CIS-telehealth is associated with less patient satisfaction than inpatient and in-person OCIC among children with similar CHRT scores.

Exploratory Aim
	

[figure not shown]
Specific Aims	Hypothesis

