4.1. Overall Design

The study conceptual framework is illustrated in Figure 1. Briefly, we have proposed an observational design. Eligible individuals will be identified during a crisis assessment, either in the emergency department or during an emergency phone or telehealth assessment. Once the individual has been assessed and assigned to the clinician for treatment, study staff will assess if the patient is appropriate for the study using the study eligibility criteria. Individuals who receive treatment in one of the following treatment arms will be eligible for this observation study: inpatient, in-person OCIC or telehealth crisis intervention service. Eligible individuals will be contacted by study staff to introduce and offer the study. If patient and guardian agree, they will complete surveys at baseline and every 2 weeks for 6 months to evaluate outcomes.

Figure 1

Clinical features will be measured with the CHRT-SR, Suicidal Event Form for START, and our short START-Clinical Features (CF) form at baseline and every two weeks (see Schedule of Events) to evaluate HTE's. A one time survey will be completed at week 2 that collects information related to the impact of COVID-19 on the family. To decrease clinician, patient, and family burden, the scales are self-report short forms. All START follow up forms will be sent to participants and guardians every 2 weeks via email prompts in REDCap and data will be collected upon return from participants. Study CRCs will make best efforts to contact families for reminder to complete data within the study milestone window, however completion at each milestone marker is not ensured due to nature of population group. Data will be collected when available. The research coordinators, a research team member, or clinicians will ensure the

completion of the Suicidal Event Form for START and the brief START-CF form based on EHR review and/or other sources of information (family and patients) within 72 hours of admission (baseline) to inpatient, telehealth CIS, or OCIC and every two weeks. The research coordinators will search the EHR for all hospitals (with permission and consent) on weekly basis for suicidal events which may have ICD-10-CM code.¹⁰⁰ We developed this plan based on feedback from patients, families, and clinicians.

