5.1. Workflow

The START Non-intervention study workflow is as follows:

- Patient presents in the ED or crisis assessment with chief complaint of suicidal ideation.
- Patients will be assessed by a mental health clinician and treatment will be determined. The CHRT-SR will be clinically obtained or during baseline data gathering at crisis assessment.
- If a patient is determined to need inpatient, in-person OCIC or telehealth CIS, they are eligible for the study and will be contacted by research staff to introduce the study.
- If patient and guardian agree to be in the study, they will be remotely consented and complete baseline surveys.
- Patient will be contacted every 2 weeks for up to 6 months to complete surveys.

Consistent with Informed Consent standard operating procedures a guardian can withdraw consent at any time in the study.

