8.2.1. Time Period and Frequency for Collecting AE and SAE Information

All AE and SAE will be collected from the start of treatment until 180 day follow-up or when the participant completes milestones.

For serious adverse events that result in injury, disability, death or significant functional impairment, each site is required to notify the DSMB and the IRB within 24-48 hours of the knowledge of the occurrence one of these SAE's, how the site personnel became aware of it, and

the response. The DSMB will make a determination as to whether the risks and benefits of the study are altered by the event.

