8.2.3. Follow-up of AE and SAE

The main adverse events (AEs) discerned during the 180 day follow-up interviews will be suicidal ideation with intent, or a recent suicide attempt. All AEs and SAEs will be documented

by the site manager and will be reported to the DSMB and IRB as needed. [name] will be notified because part of his role as overall PI of all AEs and SAEs.

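### The Schedule of Events stops at week 22 (day 154), but the text promises two-weekly surveys and outcomes to 180 days; if sites follow the schedule, the last 26 days have no scheduled event form

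*Combined protocol and SAP*

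**What the plan says.** The header of the Schedule of Events (Appendix 1, Section 11.1) reads "Baseline 2 4 6 8 10 12 14 16 18 20 22". That is 12 time points. The "Suicidal Event Form for START", the CHRT-SR, the Clinical Features form and the three PROMIS forms each carry 12 marks, the last at week 22.

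The text describes a longer follow-up:

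- Section 4.1: "they will complete surveys at baseline and every 2 weeks for 6 months to evaluate outcomes".
- Section 5.1: "Patient will be contacted every 2 weeks for up to 6 months to complete surveys".
- Section 2.3 lists among the benefits "gathering data from parents and participants every two weeks for up to 180 days".
- Section 3, Specific Aim 1, defines response partly by "a lower number of suicidal events over 90 days and 180 days". It also follows ideation severity and substance use over 180 days, as does Section 9.2.3.
- Section 8.2.3: "The main adverse events (AEs) discerned during the 180 day follow-up interviews will be suicidal ideation with intent". The schedule contains no such interview.
- Section 8.2.1: "All AE and SAE will be collected from the start of treatment until 180 day follow-up or when the participant completes milestones".

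Section 8 refers to the schedule for the timing of procedures and makes adherence to it a requirement. Sections 8 and 8.1 refer to it again when they say how time to first recurrence, the number of events and ideation severity are measured.

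**The concern.** The event outcomes depend on a form whose timetable ends before the horizon over which they are to be reported. Section 2.2 includes attempts and interrupted attempts in the definition of a suicidal event, and these need not lead to an emergency visit or admission. The weekly search of hospital records in Section 4.1 can find events that reached a searched hospital, but it depends on permission and consent and has no stated end date. For the others, the study relies on the patient or family reporting them, and the two-weekly form is the scheduled way of asking.

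If some sites stop at week 22 and others continue to six months, the way events are found changes late in follow-up and may differ between sites. The 180-day event count, any time-to-event analysis run to 180 days, and the 180-day ideation and substance use measures would all be affected.

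**Working it through.** **Length of follow-up.** The text gives 180 days. The schedule does not reproduce it:

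- Last scheduled contact: 22 × 7 = day 154.
- Shortfall: 180 − 154 = 26 days; 26 / 180 = 14.4%.
- Section 8 skips a survey not completed within 10 days of its window. Reading this as 10 days after the due date, the week 22 form could come back as late as 154 + 10 = day 164, leaving 180 − 164 = 16 days that no scheduled form can cover.
- At two-week spacing, week 24 is day 168 and week 26 is day 182. Reaching day 180 therefore takes 14 time points, not 12.

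**Which analyses are exposed.** Sections 4.2 and 9.2.3 specify the Aim 1 Cox test within 3 months. Week 12 is day 84 and week 14 is day 98, so day 90 is bracketed and that test is untouched. Section 9.2.1 gives the primary Cox model no horizon, Section 9.1 bases power on 6-month rates, and Specific Aim 1 names 180 days. Results to 180 days are exposed.

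**First events after day 154.** Inputs: 220 expected completers (Section 9.1) and 6-month risks of 10% and 19% (Section 9.1) and 27.3% (Section 2.2, preliminary data). Six months is taken as 180 days. A constant hazard is my assumption; the documents do not state one.

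Risk by day 154 = 1 − (1 − p)^(154/180). Events after day 154 = 220 × (p − risk by day 154).

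| p | Risk by day 154 | First events after day 154, of 220 |
|---|---|---|
| 0.10 | 0.0862 | 220 × 0.0138 = 3.0 |
| 0.19 | 0.1650 | 220 × 0.0250 = 5.5 |
| 0.273 | 0.2387 | 220 × 0.0343 = 7.5 |

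For inpatient against OCIC at 70 and 75 patients, expected events to day 180 are 70 × 0.19 + 75 × 0.10 = 20.8. To day 154 they are 70 × 0.1650 + 75 × 0.0862 = 18.0.

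**What these counts mean.** They are all first events after day 154, not events that would be missed. The 19% is an inpatient readmission rate, so those events are hospital events. The 27.3% includes emergency visits and admissions. The 10% is a reattempt rate and lies nearer to what could be lost. With the 8.7% reattempt rate from Section 2.2, the same formula gives about 2.7.

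Risk is also not constant in the protocol's own account. Section 2.2 says that almost half of the reattempts came within a month of discharge, and that the first month after inpatient discharge carries the greatest risk of reattempt. If half of the 8.7% fell in the first 30 days and the rest were spread evenly over the other 150 (my assumption, ignoring the difference between discharge and baseline), the last 26 days would hold 220 × 0.0435 × 26/150 = about 1.7 attempts. Some of those would reach a searched hospital.

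**The case against.** The strongest reply is that the schedule is an incomplete summary and the body of the protocol governs. Sections 2.3, 4.1 and 5.1 all run surveys to six months or 180 days. Section 8.2.3 names interviews at 180 days, Section 8.2 has adverse events reported by the participant or a caregiver and counts suicide attempts among them, and Section 4.1 lets the event form draw on the family and patient as well as on records.

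Much of this stands. A reader might infer that nothing is surveyed after day 154 and that only events in hospital records can then be found. The documents do not support that: they contradict themselves about the survey period and describe other reporting routes.

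A reader might also infer that patients will be counted as event-free to day 180 after their last form. No section says so. A Cox model allows censoring, and Section 9.2 leaves missing data to a later analysis plan.

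The reply does not remove the contradiction. Section 8 makes the schedule binding, and the 180-day interview has no place in it. The adverse event period in Section 8.2.1 may also end when milestones are complete; since Appendix 1 carries milestones in its title, that can be read as week 22.

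One caution concerns the text available to me. The last row of the table, the Self Assessment Manikin, breaks off at week 12. The header and all the two-weekly rows agree on 12 columns, so a lost week 24 column is possible but not indicated.

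**Conclusion.** The point holds as a contradiction between the schedule and the text that needs to be reconciled. If the schedule is followed, event ascertainment by form is unscheduled for 26 of 180 days, or for at least 16 if the last form is returned late. Attempts and interrupted attempts that reach no searched hospital may be missed in that period.

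The 3 to 7.5 first events in 220 are an upper bound on missed first events, given the stated risks and a constant hazard. Record review and adverse event reporting would recover some, and the early concentration of risk points lower. Repeat events, which enter the event count, are not in this figure. The matter should be settled because the correction is cheap and the 180-day outcomes depend on it.

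**What to change.** Choose one of two courses and make the schedule, Section 3 and Sections 8.2.1 and 8.2.3 agree with it.

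1. **Extend the schedule to match the text.** Add week 24 and week 26 columns (or week 24 and a day-180 contact), at least for the Suicidal Event Form, and show the 180-day interview if it is a separate contact. At the $20 per survey of Section 5.3, participant payments are at most 244 × 2 × $20 = $9,760. Staff time is additional, but the six-month text already implies it.
2. **Restate the self-report horizon as 22 weeks.** End time-to-event follow-up at a common date covered by both the form and the record search. Keep every event found by either route up to that date, and censor event-free participants at their last ascertainment up to it. Censoring everyone at the last completed form would instead discard later events found by the search. This course costs only a text change, but it gives up the 180-day self-report outcomes.

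Under either course, state the horizon of the primary Cox model, the end date of the weekly record search, and what counts as ascertainment for censoring.
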